Part 3 is a placebo-controlled, double blind, pharmacist and sponsor open, cohort to evaluate safety, tolerability, PK, immunogenicity, of repeat doses of PF-06817024 administered to subjects with moderate to severe AD. Approximately 20 subjects are planned to be enrolled in this cohort. Subjects will be randomized to receive PF-06817024 or placebo in a 3: 1 ratio (PF-06817024: placebo). Additional subjects up to a total of approximately 32 may be enrolled in a 3: 1 ratio (PF-06817024: placebo).

Subjects randomized to PF-06817024 will receive a loading dose of 600 mg IV on Day 1, followed by 3 doses of 300 mg IV every 4 weeks (last dose being on Week 12). Placebo subjects will receive 4 IV doses of matching placebo every 4 weeks. This dosing regimen is expected to decrease the time to steady state

exposure and provide nearly complete target coverage based on currently available in vitro and clinical data.

1.3.1.3. Parts 1, 2, and 3

The duration of the follow-up is selected to be at least 1 year after the last dose of study drug (at Week 12 for Part 3), which is ≥ 3 times the preliminary estimated half-life of approximately 90 days and > 80% exposure (AUC) based on emerging data for the earlier cohorts of healthy subjects, which is adequate to estimate the elimination half-life. If the emerging data project that pharmacologically relevant exposure will extend significantly longer than 1 year, the subjects will be asked to return for extended follow-up visit(s) at up to 3 month intervals beyond the last planned regular visit until one of the following criteria has been met:

• The follow up period from the last dose of study drug is approximately ≥5 times the observed half-life; OR

• The period since the last dose of study drug is of sufficient duration to have projected exposures decrease below ADA drug tolerance levels; OR

The Sponsor will inform the sites when subjects may be discharged from the study based on review of emerging data indicating that one or more of the above criteria are met. Current guidance is that subjects will be in the study for 5 half-lives ie, about 450 days from the last dose.

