7.1.1.7. Electrocardiogram

Electrocardiograms (ECGs) should be collected at times specified in the STUDY PROCEDURES section of this protocol.

All scheduled ECGs should be performed after the subject has rested quietly for at least 10 minutes in a supine position.

Triplicate 12-lead ECGs will be obtained approximately 2-4 minutes apart during clinical confinement at times specified in the SoA. Single ECGs will be collected at all other designated visits per SoA. The average of the triplicate ECG measurements collected pre-dose on Day 1 will serve as each subject's baseline QTc value. When the timing of these measurements coincides with a blood collection, the ECG should be obtained prior to the nominal time of the blood collection, blood pressure and pulse rate.

To ensure safety of the subjects, a qualified individual at the investigator site will make comparisons to baseline measurements. If the QTc interval for single ECG collections is increased by \geq 45 msec from the baseline, or an absolute QTc value is \geq 500 msec for any scheduled ECG, then 2 additional ECGs will be collected, approximately 2-4 minutes apart, to confirm the original measurement. If either of the QTc values from these repeated ECGs remains above the threshold value (\geq 45 msec from the baseline; or is \geq 500 msec), then a single ECG must be repeated at least hourly until QTc values from 2 successive ECGs fall below the threshold value that triggered the repeat measurement.

For triplicate ECGs, if the average of QTc values from the triplicate measurements remains above the threshold value (≥45 msec from the baseline; or is ≥500 msec), then a single ECG must be repeated at least hourly until QTc values from 2 successive ECGs fall below the threshold value that triggered the repeat measurement.

If QTc values remain \geq 500 msec (or \geq 45 msec from the baseline) for greater than 4 hours (or sooner at the discretion of the investigator); or QTc intervals get progressively longer, the subject should undergo continuous ECG monitoring. A cardiologist should be consulted if QTc intervals do not return to less than 500 msec (or to \leq 45 msec above the baseline) after 8 hours of monitoring (or sooner at the discretion of the investigator).

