7.1.9.1. Potential Cases of Acute Kidney Injury

Abnormal values in serum creatinine (SCr) concurrent with absence of increase in blood urea nitrogen (BUN) that meet the criteria below, in the absence of other causes of kidney injury, are considered potential cases of acute kidney injury and should be considered important medical events.

An increase of ≥ 0.3 mg/dL (or ≥ 26.5 µmol/L) in serum creatinine relative to subjects' own baseline measurement should trigger another assessment of SCr as soon as practically feasible, preferably within 48-hours from awareness

If the second assessment (after the 1st observations of \geq 0.3 mg/dL (or \geq 26.5 μ mol/L) in serum creatinine relative to subjects' own baseline measurement) is \geq 0.4 mg/dL (or \geq 35.4 μ mol/L), the subject should be discontinued from the study and adequate, immediate, supportive measures taken to correct apparent acute kidney injury

Subjects should return to the investigational site and be evaluated as soon as possible, preferably within 48-hours from awareness of the second assessment confirming abnormal SCr result. This evaluation should include laboratory tests, detailed history, and physical assessment. In addition to repeating SCr, laboratory tests should include: serum

blood-urea-nitrogen, serum creatine kinase, serum electrolytes (including at a minimum potassium, sodium, phosphate/phosphorus, calcium), in addition to urinary dipstick, urine microscopic examination, and urinary indices. All cases confirmed on repeat testing as meeting the laboratory criteria for acute-kidney-injury, with no other cause(s) of laboratory abnormalities identified should be considered as potential cases of drug-induced kidney injury irrespective of availability of all the results of the investigations performed to determine etiology of the abnormal SCr. If ≥ 2 subjects in the same cohort are noted to have $2 \ \underline{consecutive}$ SCr results of $\geq 0.3 \ mg/dL$ (or $\geq 26.5 \ \mu mol/L$), an assessment of whether the finding may be considered adverse drug reaction should be undertaken.

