7.2.1.2. Pregnancy Testing

For female subjects of childbearing potential, a serum or urine pregnancy test with sensitivity of at least 25 mIU/mL, will be performed at Screening, all study periods (Week 0, Week 1, Week 4, Week 8, Week 12, Week 16), follow-up (Week 20, Week 24, Week 36, Week 48) and extended follow-up visits. Results will be obtained prior to dosing during each period. A negative pregnancy result is required before the subject may receive the investigational product. In addition, urine pregnancy tests must be done at home by female subjects of childbearing potential at the nominal visits corresponding to Week 28, Week 32, Week 40 and Week 44 and every month between the scheduled extended visit follow-up visits. PI must be informed immediately if pregnancy test is positive and must see the PI for retesting. Pregnancy tests will also be done whenever one menstrual cycle is missed during the active treatment period (or when potential pregnancy is otherwise suspected). Pregnancy tests may also be repeated as per request of institutional review boards (IRBs)/ ethics committees (ECs) or if required by local regulations.

Pregnancy testing MUST have been performed within the permitted window and the result MUST be negative for female subjects of childbearing potential prior to dosing. Pregnancy test results will be documented in the CRF.

In the case of a positive confirmed pregnancy, the subject will be withdrawn from administration of investigational product but may remain in the study.

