7.2.5.1. Potential Cases of Acute Kidney Injury

See Section 7.1.9.1.

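### Section 7.1.9.1 words the creatinine retest threshold for discontinuation as a value of 0.4 mg/dL, not a rise from baseline; the cohort rule's 0.3 mg/dL has the same gap

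*Protocol*

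**What the plan says.** Protocol section 7.1.9.1 (Potential Cases of Acute Kidney Injury) has three creatinine steps.

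- **First trigger.** A rise of at least 0.3 mg/dL (26.5 µmol/L), "relative to subjects' own baseline measurement should trigger another assessment of SCr as soon as practically feasible".
- **Retest.** If the second assessment is at least 0.4 mg/dL (35.4 µmol/L), "the subject should be discontinued from the study and adequate, immediate, supportive measures taken to correct apparent acute kidney injury". This sentence does mention baseline, but inside a parenthesis that describes the first observation. Nothing attaches an increase or a baseline to the 0.4.
- **Cohort rule.** If two or more subjects in a cohort each have two consecutive creatinine results of at least 0.3 mg/dL (26.5 µmol/L), "an assessment of whether the finding may be considered adverse drug reaction should be undertaken". No baseline is mentioned.

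For Part 3, section 7.2.5.1 says only "See Section 7.1.9.1", so the same wording applies there. SAP section 6.2.2 refers laboratory abnormalities to the sponsor's reporting standards and gives no creatinine rule.

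**The concern.** Only the first of the three thresholds is written as a change. The other two are written as concentrations, at levels that ordinary creatinine values would exceed.

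The retest is there to tell a transient rise from a sustained one. With the 0.4 taken as a value, a repeat that is fully back at baseline still calls for discontinuation. The action is leaving the study, not only stopping the drug, and the primary endpoints are safety findings through the end of the study. A subject removed in error would lose remaining doses and scheduled safety visits. The cohort rule, read the same way, would be met by unchanged results and would carry no renal signal.

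**Working it through.** **Units.** The two unit pairs imply factors of 26.5/0.3 = 88.3 and 35.4/0.4 = 88.5, which agree within rounding. With an assumed factor of 88.4, 0.3 × 88.4 = 26.5 and 0.4 × 88.4 = 35.4 µmol/L, as the protocol states. The numbers are consistent; what is missing is the reference to baseline.

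**Literal and rise readings.** Let b be the subject's baseline in mg/dL.

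- Retest, literal: discontinue if the repeat ≥ 0.4. As a rise: discontinue if the repeat ≥ b + 0.4.
- Cohort, literal: two consecutive results ≥ 0.3. As a rise: two consecutive results ≥ b + 0.3.

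In both cases the readings differ by exactly b. A repeat equal to b meets the literal retest limit whenever b ≥ 0.4. Two unchanged results meet the literal cohort limit whenever b ≥ 0.3.

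**Illustration.** The documents give no creatinine levels, so the baselines below are assumptions. The first value is b + 0.3 and the repeat is back at b. To be cleared literally, the repeat must fall below baseline by more than b − 0.4, which is (b − 0.4)/b of baseline.

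| Assumed b | First value | Repeat | Literal ≥ 0.4? | Rise limit b + 0.4 | Rise limit met? | Fall below b needed to clear literally (more than) |
|---|---|---|---|---|---|---|
| 0.6 | 0.9 | 0.6 | yes | 1.0 | no | 0.2 (33%) |
| 0.8 | 1.1 | 0.8 | yes | 1.2 | no | 0.4 (50%) |
| 1.0 | 1.3 | 1.0 | yes | 1.4 | no | 0.6 (60%) |
| 1.2 | 1.5 | 1.2 | yes | 1.6 | no | 0.8 (67%) |

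For the cohort rule, the rise reading needs 0.9, 1.1, 1.3 or 1.5 mg/dL twice in a row at these baselines. The literal reading needs only 0.3.

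**Cost of one wrong discontinuation in Part 3.**

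- At Day 8, the doses on Days 29, 57 and 85 are lost: 3 × 300 = 900 mg of a planned 600 + 900 = 1500 mg.
- At Day 113, the four visits on Days 141, 169, 253 and 337 are lost. Section 1.3.1.3 states "Current guidance is that subjects will be in the study for 5 half-lives ie, about 450 days from the last dose". The last dose is on Day 85, so planned follow-up runs to about Day 85 + 450 = Day 535, and up to about 535 − 113 = 422 days would be forgone.

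**Comparison with other rules.** The QTc rule (sections 7.1.1.7 and 7.2.1.7) restates the 45 msec change from baseline at the repeat step and continues until "QTc values from 2 successive ECGs fall below the threshold value that triggered the repeat measurement". The liver rule (section 8.6.2) also refers to baseline for subjects whose starting values are abnormal. Neither section 7.2.5.1 nor SAP section 6.2.2 supplies the missing words for creatinine.

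**The case against.** The strongest reply is that the context rules out the literal reading. The section opens by limiting itself to abnormal creatinine values with no other cause of kidney injury. The 0.4 sentence applies only after a rise from baseline has been seen. The purpose given is to correct apparent injury, and the next paragraph speaks of "awareness of the second assessment confirming abnormal SCr result". A repeat back at a normal baseline confirms nothing. The parenthesis itself restates the first trigger without the word increase, so the bare 0.4 and 0.3 look like continued shorthand. This stands as evidence of intent, and a site reading the whole section would probably apply rises. It does not make the sentence correct as an instruction.

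Second, the loss of follow-up is only partial. Section 6.2.6 asks for every effort to complete an early withdrawal visit with safety laboratory tests and for follow-up of unresolved adverse events. Section 8.1 allows follow-up until an event resolves or stabilises, and section 7.1.9.1 itself calls for a site evaluation after the second result. This stands: the doses and days above are upper limits on the cost of a misreading to which no probability is attached.

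Third, whether confirmed kidney injury should end study participation or only dosing is a separate design choice. After a confirmed pregnancy, section 7.2.1.2 says "the subject will be withdrawn from administration of investigational product but may remain in the study", which shows that the protocol has a milder action available. That comparison does not bear on whether the threshold is correctly worded, and the change proposed here leaves the choice as it is.

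Fourth, no analysis depends on these limits, the cohort rule triggers only an assessment, and the sponsor's reporting standards are not available to check. All of this limits the weight of the point.

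**Conclusion.** The point holds, as a minor one. Two decision thresholds in section 7.1.9.1 lack the baseline reference that the first trigger has, and no other text supplies it. Followed exactly, the retest would discontinue a subject whose creatinine had returned to any baseline of 0.4 mg/dL or more, and unchanged results of 0.3 mg/dL or more would meet the cohort limit. Those statements follow from the wording alone; only the illustrated baselines are assumed. No trigger probability is claimed, because the documents give neither a creatinine level nor its variability. The 0.4 threshold matters more, because it leads to leaving the study. This is a drafting error in a safety rule, and it changes no planned estimate or test.

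**What to change.** In section 7.1.9.1, state both limits as changes:

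- Retest: the second assessment shows an increase of at least 0.4 mg/dL (35.4 µmol/L) over the subject's own baseline.
- Cohort rule: two consecutive results, each showing an increase of at least 0.3 mg/dL (26.5 µmol/L) over the subject's own baseline.

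The clinical team should confirm that this is the intent. Part 3 follows through the cross-reference in section 7.2.5.1. The cost is one phrase in each of two sentences, issued as a protocol clarification or site letter, with no added test, visit or patient.

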7.1.16. Endoscopy (Part 2 only)

A nasal endoscopy is to be completed during the screening period per SoA Table D. A qualified ear, nose, and throat (ENT) physician is to complete the nasal endoscopy and endoscopic nasal polyp score (NPS) to determine study eligibility.

7.1.16.1. Nasal Polyp Score (Part 2 only)

The NPS used to assess eligibility for inclusion in this study is a modified version of the staging system proposed by the Rhinosinusitis Initiative in 2006, ⁴⁴ as used in studies of nasal steroids, ⁴⁵ dupilumab, ⁴⁶ omalizumab, ⁴⁷ reslizumab, ⁴⁸ and mepolizumab ⁴⁹ in CRSwNP. The NPS is to be completed and calculated by an ENT physician (see Appendix 3).

7.2. Part 3

PF-06817024

7.2.1. Safety

7.2.1.1. Laboratory Tests

The following safety laboratory tests will be performed at times defined in the STUDY PROCEDURES section of this protocol. Additional laboratory results may be reported on these samples as a result of the method of analysis or the type of analyzer used by the clinical laboratory; or as derived from calculated values. These additional tests would not require additional collection of blood. Unscheduled clinical labs may be obtained at any time during the study to assess any perceived safety concerns. Abnormal safety labs maybe repeated at investigator's discretion. Safety labs maybe collected by standard phlebotomy or from the IV catheter.

Table 7. Laboratory Tests

Hematology	Chemistry	Urinalysis	Other
Hemoglobin	BUN/urea and Creatinine	pН	FSH ^{b,f}
Hematocrit	Glucose (fasting)	Glucose (qual)	HCG ^c
RBC count	Calcium	Protein (qual)	Urine drug screening ^{f,g}
MCV	Sodium	Blood (qual)	HIV, HBsAg, HBcAb,
MCH	Potassium	Ketones	and HCVAb ^{e,f}
MCHC	Chloride	Nitrites	HBsAb ^d
Platelet count	Total CO ₂ (Bicarbonate)	Leukocyte esterase	QuantiFERON-TB Gold
WBC count	AST, ALT	Urobilinogen	Test ^f
Total neutrophils	Total Bilirubin	Urine bilirubin	
(Abs)	Alkaline phosphatase	Microscopy ^a	
Eosinophils (Abs)	Uric acid		
Monocytes (Abs)	Albumin		
Basophils (Abs)	Total protein		
Lymphocytes (Abs)	-		
	Additional Tests (Needed		
	for Hy's law)		
	AST, ALT (repeat)		
	Total bilirubin (repeat)		
	Albumin (repeat)		
	Alkaline phosphatase		
	(repeat)		
	Direct bilirubin		
	Indirect bilirubin		
	Creatine kinase		
	GGT		
	PT/INR		

- a. Only if urine dipstick is positive for blood, protein, nitrites or leukocyte esterase.
- b. At Screening only, in females who are amenorrheic for at least 12 consecutive months.
- c. Serum or Urine HCG (human chorionic gonadotropin) (sensitivity of ≤25 mIU/mL) for female subjects of childbearing potential.
- d. HBsAb test if screening results for HBsAg are negative and HBcAb are positive.
- e. HCV RNA test will be done as a reflex for positive HCVAb test.
- f. At screening.
- g. At Day 1.

- Minimum requirement for drug screening includes: cocaine, opiates/opioids, benzodiazepines and amphetamines.
- Subjects may undergo random urine drug screening at the discretion of the investigator. Drug screening conducted prior to dosing must be negative for subjects to receive study medication. If urine drug test result at baseline is not available, subject with a negative drug test result at screening may be dosed if the subject has no prior history of drug abuse.
- Any remaining serum/plasma from samples collected for clinical safety labs at baseline may be retained for at least 2 years from the time of collection or 1 year after the completion of the study (whichever comes first), after which they can be discarded.

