- 8. Have active chronic or acute skin infection (except latent TB infection see Inclusion Criterion 4 and 5 in Section 4.1.1.1) requiring treatment with systemic antibiotics, antivirals, antiparasitics, antiprotozoals, or antifungals within 2 weeks prior to Day 1, or superficial skin infections within 1 week prior to Day 1. NOTE: potential subjects may be rescreened after infection resolves.
- 9. Subjects with a history of helminthic infestation or resident/recent travel from an endemic area within 90 days prior to Screening
- 10. Have a known immunodeficiency disorder or a first-degree relative with a hereditary immunodeficiency.
- 11. Have undergone significant trauma or major surgery within 1 month of the first dose of study drug.
- 12. Subjects will be screened for Hepatitis B virus infection and will be excluded if positive for Hepatitis B surface antigen (HBsAg). Subjects with HBsAg negative testing but who test positive for hepatitis B core antibody (HBcAb) must have further testing for hepatitis B surface antibody (HBsAb). If HBsAb is negative, the subject will be excluded from the study
- 13. Subjects positive for HCVAb are to be excluded unless known to have been treated with a known curative therapy and negative for HCV CCI.
- 14. Human immunodeficiency virus (HIV) positive subjects will be excluded.
- 15. Recent exposure to live or attenuated vaccines within 28 days of the screening visit.
- 16. Subjects with a history of anaphylaxis with the following exceptions: subjects with sensitivity and/or anaphylaxis only to a single, avoidable allergen (eg, aspirin, penicillin, sulfadrugs, nonsteroidal anti-inflammatory drugs (NSAIDs), peanuts) may be enrolled, if in the opinion of the investigator, the subject is aware of the hypersensitivity and avoids -the problematic allergen. Subjects must carry appropriate treatment for anaphylaxis and must know how to manage the anaphylactic reactions.
- 17. Subjects with a fever within 7 days prior to dosing.
- 18. A positive urine drug screen except marijuana where use is permitted by local law and regulations (see Section 7.1.1.1).
- 19. History of regular alcohol consumption exceeding 7 drinks/week for females or 14 drinks/week for males; (1 drink = 5 ounces of wine or 12 ounces of beer or 1.5 ounces of hard liquor) within 6 months of Screening.

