4.2. Randomization Criteria

Subjects will be randomized into the study provided they have satisfied all subject eligibility criteria.

Part 1

Subjects will be randomized into the study provided they have satisfied all subject eligibility criteria. Subjects will be randomized within each cohort to receive either PF-06817024 (PF) or placebo (Pbo) as described in Section 3.1. The randomization ratio in the study will be 6:2 (PF:Pbo) for Cohorts 1 through 7. If additional Cohorts 10 through 12 are required, the randomization ratio in these cohorts will also be 6:2 (PF:Pbo).

Part 2

Subjects in Cohorts 8 and 9 will be randomized in either a 1: 1 or 2: 1 (PF-06817024: placebo) ratio, depending on the number of cohorts and the emerging data. Up to approximately 10 active (per dose) and approximately 15 placebo (overall) subjects will be enrolled in Part 2.

Part 3

Subjects will be randomized in an approximately 3: 1 (PF-06817024: placebo) ratio. Approximately 20 subjects are planned to be enrolled into a single cohort in Part 3. Additional subjects up to a total of approximately 32 may be enrolled in a 3: 1 ratio (PF-06817024: placebo) based on analysis of emerging safety, PK, CCI data.

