- Insert IV catheter for blood collection.

Note: Site may insert IV catheter for blood sample collection up to 24 hours prior to study drug administration only for subject who will be admitted to the clinical site a day prior to dosing. IV catheter for blood sampling may be replaced with phlebotomy procedures at the investigator's discretion. All blood samples for laboratory testing must be drawn from the extremity contralateral to that into which test article will be administered. If an indwelling catheter is used, heparin is not to be utilized to maintain patency.

- Collect blood and urine samples for the following:
 - Safety laboratory tests: Safety laboratory tests include Hematology, Chemistry, and Urinalysis (following at least a 4-hour fast). The available results must have no clinically significant findings, as judged by the investigator, in order for a subject to be dosed. Results for most laboratory tests collected on the visit day likely will not be available on the same day for review before dosing, in which case the available laboratory tests will only consist of those from the previous visit. All such laboratory results must be reviewed prior to dosing. Pregnancy testing MUST have been performed within the permitted window and the result MUST be negative for female subjects of childbearing potential prior to dosing.
 - Urine Drug Test and Alcohol Breath Test (Day 1).
 - Pharmacokinetic analysis.

- Immunogenicity (ADA, NAb) blood sampling.
- Pregnancy test for female subjects of childbearing potential.
- Urine Drug Test and Alcohol Breath Test (Day 1 only).
- Perform AD assessments: Fitzpatrick skin type assessment (Day 1 only),
- Obtain information regarding the use of prior treatment and the occurrence of adverse events.
- Contraception check.

 After all pre-dose procedures have been completed, insert IV catheter for study drug infusion (IV cohorts only) and administer the study treatment (see STUDY TREATMENTS and Administration Sections).

After dosing, the following procedures will be completed at the time(s) indicated in the SoA:

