7.1.1. Safety

7.1.1.1. Laboratory Tests

The following safety laboratory tests will be performed at times defined in the STUDY PROCEDURES section of this protocol. Additional laboratory results may be reported on these samples as a result of the method of analysis or the type of analyzer used by the clinical laboratory; or as derived from calculated values. These additional tests would not require additional collection of blood. Unscheduled clinical labs may be obtained at any time during the study to assess any perceived safety concerns.

Table 4. Laboratory Tests

PF-06817024

Hematology	Chemistry	Urinalysis	Other
Hemoglobin	BUN/urea and Creatinine	рН	FSH ^b
Hematocrit	Glucose (fasting)	Glucose (qual)	HCG ^c
RBC count	Calcium	Protein (qual)	Urine drug screening ^d
MCV	Sodium	Blood (qual)	HIV, HBsAg, HBcAb,
MCH	Potassium	Ketones	and HCVAb ^e
MCHC	Chloride	Nitrites	HBsAb ^f
Platelet count	Total CO ₂ (Bicarbonate)	Leukocyte esterase	Phadiatop ^e
WBC count	AST, ALT	Urobilinogen	QuantiFERON-TB Gold
Total neutrophils	Total Bilirubin	Urine bilirubin	Test ^e
(Abs)	Alkaline phosphatase	Microscopy ^a	
Eosinophils (Abs)	Uric acid		
Monocytes (Abs)	Albumin		
Basophils (Abs)	Total protein		
Lymphocytes (Abs)			
	Additional Tests (Needed		
	for Hy's law)		
	AST, ALT (repeat)		
	Total bilirubin (repeat)		
	Albumin (repeat)		
	Alkaline phosphatase		
	(repeat)		
	Direct bilirubin		
	Indirect bilirubin		
	Creatine kinase		
	GGT		
	PT/INR		

- a. Only if urine dipstick is positive for blood, protein, nitrites or leukocyte esterase.
- b. At Screening only, in females who are amenorrheic for at least 12 consecutive months.
- c. HCG (human chorionic gonadotropin) for female subjects of childbearing potential who have a documented bilateral tubal ligation or bilateral salpingectomy (Part 2 only)
- d. At Screening, Day 0, and Day 31 (screening and Day 0 only for SAD cohorts).
- e. At screening only. Phadiatop collection for Part 1 only; starting with Cohort 5 and later, Phadiatop is to be collected prior to dosing.
- f. HBsAb test if screening results for HBsAg are negative and HBcAb are positive (for Part 1 (Cohort 5 and later) and Part 2.
 - *Part 1*: Minimum requirement for drug screening includes: cocaine, tetrahydrocannabinol (THC), opiates/opioids, benzodiazepines and amphetamines.
 - *Part 2*: Minimum requirement for drug screening includes: cocaine, opiates/opioids, benzodiazepines and amphetamines.

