5.7. Treatment Misallocations

All analyses will be performed on an "as-treated" basis and will not include data from subjects who are randomized but not treated.

If a subject takes a treatment that is not consistent with the treatment they are randomized to, for example takes a treatment out of sequence or takes the same treatment twice, then they will be reported under the treatment that they actually receive for all safety, PK and analyses, where applicable.

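### Part 3 exclusion criterion 18 tolerates a marijuana-positive drug screen where use is lawful, but section 7.2.1.1 requires a negative screen before dosing with no exception, so the two rules must be reconciled

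*Protocol*

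**What the plan says.** **Eligibility.** Protocol 4.1.2.1, criterion 18 for Part 3, excludes "A positive urine drug screen except marijuana where use is permitted by local law and regulations (see Section 7.1.1.1"). Section 4.2 makes randomisation depend on eligibility alone: "Subjects will be randomized into the study provided they have satisfied all subject eligibility criteria".

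**Dosing.** Section 7.2.1.1, the Part 3 laboratory section, adds a separate condition: "Drug screening conducted prior to dosing must be negative for subjects to receive study medication". It exempts no substance. Its only relaxation is for a missing result: "If urine drug test result at baseline is not available, subject with a negative drug test result at screening may be dosed", provided there is no history of drug abuse.

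**Panel.** Section 7.2.1.1 sets a floor for what is tested: "Minimum requirement for drug screening includes: cocaine, opiates/opioids, benzodiazepines and amphetamines". THC is not on it.

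**The cited section.** Section 7.1.1.1 belongs to Parts 1 and 2. Its Part 1 panel is "cocaine, tetrahydrocannabinol (THC), opiates/opioids, benzodiazepines and amphetamines", and its Part 2 panel omits THC. It carries the same unqualified dosing sentence as 7.2.1.1.

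**Timing.** The drug test is done at screening (6.2.1 and Schedule of Activities Table E) and again before the first dose (6.2.2: "Urine Drug Test and Alcohol Breath Test (Day 1 only").

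**Analysis.** SAP 5.7 makes all analyses as-treated and says they "will not include data from subjects who are randomized but not treated". SAP 5.1 defines the full analysis set as everyone randomised.

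**The concern.** Two current rules answer the same question differently. Criterion 18 lets in a subject whose screen is positive only for marijuana, where local law allows it. The dosing sentence in 7.2.1.1 refuses study drug to that subject. A site that follows both admits someone it may not treat.

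The cross-reference does not resolve this. A reader who follows criterion 18 to 7.1.1.1 finds a section for other parts of the study, a Part 1 panel that includes THC, and the same unqualified dosing sentence.

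At stake is the loss of an eligible subject from a cohort of about 20, or up to about 32, in which the placebo group is very small. If the loss came after randomisation, it would also raise the question of which analysis sets still count the subject.

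**Working it through.** The plan gives no figure to reproduce. The Part 3 sample size rests on clinical considerations (Protocol 9.1), and no hypothesis is tested (SAP 4.1). The check is a comparison of texts, followed by simple arithmetic on size.

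**1. The rules applied to one subject, positive for marijuana only, where use is lawful**

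| Step | Source | Result |
|---|---|---|
| Eligible? | Protocol 4.1.2.1, criterion 18 | Not excluded |
| May be randomised? | Protocol 4.2 | Yes, if the other criteria are met |
| May be dosed? | Protocol 7.2.1.1 | No |
| Does the missing-result relaxation help? | Protocol 7.2.1.1 | No: a result exists, and the relaxation needs a negative screening test |
| Does the cited section help? | Protocol 7.1.1.1 | No: same dosing sentence |

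**2. When the conflict arises.** It needs a panel that includes THC. The Part 3 list is a minimum, so a site may test for more, but nothing says that any site does. The exception in criterion 18 has a use only if marijuana can be detected. That is an inference from the text, not a statement in it.

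**3. When it would be noticed.** The screening test is itself done before dosing, so a positive result shows the conflict at that visit. Section 3.1.3 puts baseline assessments before randomisation and first dose. Section 6.2 allows the pre-dose drug test on the preceding day, and 6.2.2 repeats the eligibility review on Day 1. No passage requires randomisation to wait for the Day 1 result, so discovery after randomisation is possible but is not the natural course.

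**4. What happens in the analysis if the subject is already randomised.** The safety and immunogenicity sets need at least one dose (SAP 5.4, 5.5), and the PK sets need treatment and data (SAP 5.2). SAP 5.7 leaves the subject out of the as-treated analyses. SAP 5.1 still counts the subject in the full analysis set, and SAP 8.1.3 reports disposition.

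**5. Share represented by one subject.** The SAP's study schematic gives 15:5 at 20 subjects. At 32 subjects, 3:1 gives 24:8.

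- Whole cohort: 1/32 = 3.1%; 1/20 = 5.0%.
- Active arm: 1/24 = 4.2%; 1/15 = 6.7%.
- Placebo arm: 1/8 = 12.5%; 1/5 = 20.0%.

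SAP 2.3 notes 28 enrolled. An exact 3:1 split would be 21:7, so one placebo subject would be 1/7 = 14.3%. That split is an assumption, because the SAP says subjects under amendment 4 were randomised 2:1.

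**6. How many subjects.** The documents give no rate of marijuana-positive results. Let q be the assumed share of subjects who test positive for THC where use is lawful. For 20 subjects the expected number barred from dosing is 20q, and the chance of at least one is 1 − (1 − q)^20.

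| Assumed q | Expected of 20 | Chance of at least one |
|---|---|---|
| 2% | 0.4 | 33% |
| 5% | 1.0 | 64% |
| 10% | 2.0 | 88% |
| 20% | 4.0 | 99% |

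These are ceilings for each q. They assume that every site tests for THC and that 7.2.1.1 is always applied as written, and they ignore replacement. They count subjects barred from dosing, not subjects lost after randomisation.

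**The case against.** The strongest reply is that this is a wording slip with little practical reach. On the Part 3 minimum panel THC is not tested and no conflict arises. The THC panel in 7.1.1.1 is labelled Part 1 and does not govern Part 3, so the wrong cross-reference alone does not change who is dosed. Subjects who withdraw may be replaced (Protocol 6.2.6 and 9.1). The study is descriptive, and a subject never dosed has no post-dose data to lose. All of this stands, and it limits the size of the problem. It does not remove the contradiction: the list is only a minimum, and wherever THC is tested and use is lawful the two rules give opposite answers.

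A reader might infer three stronger things, none of which the documents support.

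- **That randomised subjects will be refused drug and vanish from every analysis.** Testing begins at screening and baseline assessments precede randomisation, so loss before randomisation is more likely. SAP 5.1 also keeps all randomised subjects in the full analysis set.
- **That the contradiction is what makes eligibility differ between sites.** Criterion 18 itself varies with local law, so part of that difference would remain after reconciliation if the exception is kept.
- **That the arms are biased against each other.** Site staff are blinded to treatment (Protocol 5.2), and refusal would rest on a pre-dose urine result, so no link to arm is shown.

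**Conclusion.** The point holds as an internal inconsistency of minor weight. Criterion 18 and the dosing sentence in 7.2.1.1 cannot both be followed for a subject positive only for marijuana where use is lawful, and criterion 18 points to the wrong section. This is more than clerical, because the two rules disagree on whether an admitted subject may be treated.

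The practical effect depends on a site testing for THC, which the Part 3 minimum does not require, and on a positive rate that the documents do not give. With replacement allowed and loss before randomisation the likelier course, the expected effect is small. That is a judgement, not a computed result. Because the cohort is small, a single loss after randomisation would still be visible, above all in a placebo group of 5 to 8.

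**What to change.** Reconcile criterion 18 in Protocol 4.1.2.1 with the dosing sentence in 7.2.1.1, so that one rule on marijuana applies both at screening and before dosing. Change the cross-reference in criterion 18 from 7.1.1.1 to 7.2.1.1. Which rule applies is for the sponsor and investigators to decide. The cost is one clause and one cross-reference. It would also help to say in the SAP how the full analysis set in 5.1 is used, given that 5.7 leaves untreated subjects out of all analyses; that takes one sentence.
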